Research questions and objectives	
Primary objective
 
To describe utilization of systemic glucocorticoids (e.g., dexamethasone, prednisolone, methylprednisolone or hydrocortisone) for treatment of COVID-19 in two types of setting: hospitalized (in hospital care) and ambulatory (any care received outside the hospital) within 90 days following COVID-19 diagnosis.
 
Secondary objectives
 
 1. To describe at COVID-19 diagnosis date the demographic, health and clinical patient characteristics (stratified by setting and systemic glucocorticoid user type (naive, prevalent)). 2. To quantify the crude and adjusted incidence rates and time to onset of adverse events of interest (i.e., infections, hyperglycaemia, hypertension, gastrointestinal bleeding and composite cardiovascular disease events) within 30 and 90 days post treatment index date, by setting, in various treatment groups, systemic glucocorticoid user type (naive, prevalent) and sub-populations of special interest. 3. To quantify the crude and adjusted incidence rates of mortality and other disease outcomes within 30- and 90-days post treatment index date, by setting, in various treatment groups, systemic glucocorticoid

	user type (naive, prevalent) and sub-populations of special interest.
	4. To explore the performance of different coding definitions for COVID-19 and how they influence the size of the cohort
Country(-ies) of study	Belgium, France, Germany, UK, Italy, Netherlands, Spain
Author	E-CORE Network

List of Tables

Table 1 Data lock point for each available database.....	24
Table 2 Exposures of interest	28
Table 3 Calculation of duration of use and end of treatment across databases	30

List of Figures

Figure 1 Study design	23
-----------------------------	----

Table of contents

Section 1.0	Responsible Parties	8
Section 2.0	Abstract	9
Section 3.0	Amendments and Updates	14
Section 4.0	Milestones	16
Section 5.0	Rationale and Background	17
Section 6.0	Research Questions and Objectives	19
6.1	Aim	19
6.2	Primary Objective	19
6.3	Secondary Objectives	19
Section 7.0	Research Methods	21
7.1	Study Design	21
7.2	Setting	23
7.2.1	Study Time Period	23
7.2.2	Patient Selection	24
7.2.3	Follow-up	25
7.2.4	Subgroups	25
7.3	Variables	26
7.3.3	Adverse events	32
7.3.4	Disease severity outcomes	33
7.3.5	Other Variables	33
7.4	Data Sources	34
7.5	Sample Size	36
7.6	Data Management	37
7.7	Data Analysis	37
7.7.1	General considerations	37

Pharmaco- and Device Epidemiology
University of Oxford
United Kingdom
[contact]
E-mail: [contact]

Subject matter expertise

[name]
University of Hertfordshire
United Kingdom
Email: [contact]

Section 2.0 Abstract

Section	Description
Title	Systemic glucocorticoids in the treatment of COVID-19 and risks of adverse outcomes in COVID-19 patients, within primary and secondary care settings
Rationale and background	
Approximately 10-20% of COVID-19 positive patients, many of whom are older or have co-morbidities, suffer from pneumonia and acute respiratory distress syndrome (ARDS), requiring hospitalization and ventilatory support. It has been suggested that this population is also at higher risk of inflammatory immune system disorders. As a result, current treatment recommendations are to combine anti-viral therapy with immunosuppressive or immunomodulatory drugs to mitigate these immunologic complications, reducing COVID-19 associated morbidity and mortality. While the search for appropriate anti-viral therapy is ongoing, there have been some positive results with respect to systemic glucocorticoid use, such as dexamethasone, which has been associated with reduced mortality in ventilated patients and those on supplemental oxygen therapy. This has mobilised efforts to repurpose some of these steroids for the treatment of severe COVID-19 cases. That said, a lot of information on steroid use in COVID-19 patients is currently missing. Treatment type, dosage, timing of administration, as well as identification of patient risk groups that will benefit most from the treatments, is inadequately explored. To partially address these research gaps, this protocol describes a non-comparative study to explore patterns of systemic glucocorticoid use and administration in patients with either a first confirmed diagnosis for COVID-19 (diagCOVID-19) or a first positive PCR test for SARS-CoV-2 (labCOVID-19) using healthcare databases from seven European countries.

Research question and objectives	
The aim of this study is to describe patterns of systemic glucocorticoid use, as well as the risks of adverse events associated with these medications, in diagCOVID-19 or labCOVID-19 patients across seven European countries in ambulatory and hospital inpatient care settings.
 
Primary Objective: To describe utilization of systemic glucocorticoids (e.g., dexamethasone, prednisolone, methylprednisolone or hydrocortisone) for treatment of COVID-19 in two settings: hospitalized (in hospital care) and ambulatory (any care received outside of hospital) within 90 days following COVID-19 diagnosis. The following variables will be described:

- Prevalent use or naïve (incident) use of systemic glucocorticoids at date of diagnosis of COVID-19
- Concomitant use of other medications (number and type) and invasive/non-invasive respiratory support during follow up
- Type of systemic glucocorticoid received
- Time to systemic glucocorticoid initiation from COVID-19 diagnosis
- Route of administration
- Systemic glucocorticoid daily dose at initiation (treatment index date), cumulative duration, distribution of duration of use and cumulative dose of systemic glucocorticoid received
- For prevalent users: proximity of previous glucocorticoid use to COVID-19 diagnosis (current use (concomitant on date of COVID-19 diagnosis, recent use (between 15-30 days before date of COVID-19 diagnosis) or remote use (use ended more than 30 days before date of COVID-19 diagnosis))

Secondary Objectives:

1. To describe **at COVID-19 diagnosis date and at treatment index date** the demographic, health and clinical patient characteristics). The following variables will be described:
 - demographics
 - comorbidities (number and type)
 - symptoms (number and type) preceding and/or on the date of diagnosis the diagnosis if captured
 - time from onset of COVID-19 illness symptoms to confirmed diagnosis date

Some of these characteristics will be stratified by setting, glucocorticoid exposure type (naïve, prevalent) and subgroups of special interest (e.g., chronic cardiac and pulmonary disease, diabetes, renal insufficiency).

2. To quantify the crude and adjusted incidence rates and time to onset of adverse events of interest (e.g., infections, hyperglycaemia, GI bleeding, composite of cardiovascular disease events) within **30 and 90 days post treatment index date**, in various treatment groups, stratified by setting, glucocorticoid exposure type (naïve, prevalent) and subgroups of special interest.
3. To quantify the crude and adjusted incidence rates of mortality and other disease outcomes within **30 and 90 days post treatment index date**, in various treatment

	
groups, stratified by setting glucocorticoid exposure type (naive, prevalent) and subgroups of special interest.
 
4. To explore the performance of different coding definitions for COVID-19 and how they influence the size of the cohort

Study design	This is a PASS study using a descriptive cohort study design using secondary data sources (electronic medical records).
Setting	COVID-19 diagnosed patients across primary and secondary care settings in seven European Countries (Belgium, France, Italy, Netherlands, Germany, United Kingdom, Spain), with the study time period from 1 st January 2020 to 1 st January 2021 (at the latest), will be considered for analysis. Cut-off dates for data inclusion i.e. data lock points will vary based on the country and database used. Four different cohorts based on healthcare setting (ambulatory or hospital setting) and systemic glucocorticoid user type (naïve or prevalent) will be created. Index dates, outcomes and follow-up censoring vary per objective and will be appropriately applied in the analyses.
Variables	
COVID-19 Case Definition
 
 • Main analysis: Catch-all definition based on the earliest of a first diagnosis confirmed for COVID-19 or first SARS-CoV-2 positive PCR test 
Secondary Objective 4 alternative definitions: Diagnosis confirmed (diagCOVID-19), laboratory confirmed (labCOVID-19), symptomatic COVID-19 and suspected COVID-19 cases
 
Exposure (based on prescription data)
 
 • Glucocorticoids used in COVID-19 indication glucocorticoid (dexamethasone, prednisolone, prednisone, methylprednisolone or hydrocortisone) • Glucocorticoid for pre-existing conditions, described by metrics such as proportion of days covered in lookback period and recent use of medication based on prescription records. • Other COVID-19 treatments (e.g., antiviral, antibiotic, statin therapy) • Respiratory support 
These will be further characterized using specific criteria and formula for dose and duration.
 
For secondary objectives 2 and 3 where the index date is based on treatment, the treatment exposure groups will be categorized as follows:

- Use of systemic glucocorticoids without other treatments for COVID-19
- Use of systemic glucocorticoids plus other treatments for COVID-19
- Only other treatments and respiratory support with no systemic glucocorticoids
- No specific treatments for COVID-19 infection

Outcomes (Secondary objectives 2 and 3)

- Adverse events: composite cardiovascular events, hypertension, arrhythmia, gastritis, gastric ulcer, GI bleed, psychosis, myopathy, hyperglycaemia and any bacterial viral, fungal and parasitic infection
- Disease severity:
 - Ambulatory: Hospital admission, venous thromboembolism or pulmonary embolism, disseminated intravascular coagulation, death of any cause
 - Hospital: Intensive services as an outcome in inpatient cohorts (including mechanical ventilation and Extracorporeal membrane oxygenation (ECMO)), venous thromboembolism or pulmonary embolism, disseminated intravascular coagulation, discharge from hospital, death of any cause

Demographic and clinical variables: age, sex, month of diagnosis, comorbidities

Data sources

Ambulatory:

- Belgium, France, Italy – Longitudinal Patient Database (IQVIA)
- Germany – Disease Analyser (IQVIA)
- United Kingdom – IQVIA Medical Research Data (IMRD) UK
- The Netherlands – Integrated Primary Care Information (IPCI)
- Spain – Information System for Research in Primary Care (SIDIAP) as primary care databases

Hospital:

- Hospital de Madrid Hospitales

Data analysis

Continuous variables will be described using mean, standard deviation, median, first and third quartiles, minimum, and maximum. Categorical variables will be described by the number and percentage of patients in each category. Patterns of missingness will be reported and 95% confidence Intervals will be presented. The

results for each country and where available, each setting will be presented separately.

Primary Objective:

- Descriptive analysis for systemic glucocorticoid use patterns will be carried and stratified by setting, glucocorticoid exposure type (naive, prevalent) and subgroups of special interest.
- Kaplan-Meier methods will be used to estimate time to systemic glucocorticoid initiation from COVID-19 diagnosis, stratified by route of administration (oral vs intravenous).

Secondary Objective 1:

- Cohort-specific descriptive statistics summarizing demographic, health and clinical patient characteristics, stratified by setting, glucocorticoid exposure type glucocorticoid (naive, prevalent), and subgroups of special interest will be presented.

Secondary Objectives 2 and 3:

- Crude incidence (presented as both proportions and rates) for the relevant outcomes for each of the treatment exposure groups will be calculated.
- The cumulative incidence rates will be reported at the end of follow-up (30 and 90 days).
- Data will be stratified by setting, glucocorticoid exposure type (naive, prevalent), and subgroups of special interest
- Cox regression models (using multivariable models and using PS adjustment) will be used to compute the adjusted incidence rates.

Secondary Objective 4:

- The performance of different COVID-19 disease definitions based on rule-based phenotype algorithms will be explored using diagnostic predictive modelling

**Plans for
Disseminating
and
Communicating
Study Results**

IQVIA will produce a study report in accordance with the GVP guidelines VIII (EMA/813938/2011). Study information (including protocol and final report) will be added in the EU PAS register.

Section 3.0 Amendments and Updates

Major and Minor Amendments	
Major Amendments	Minor Amendments

 None 	
 Abstract section Appendix 3 Misspellings and editorial checks across the entire document

Number	Date	Section of the Amendment or update Protocol	Reason
1	30th October 2020	Throughout document	Amended drug name from corticosteroids to glucocorticoids Recommendation from reviewer to capture narrower term
2	30th October 2020	2.0	Re-aligned with the updated protocol. Editorial checks
3	30th October 2020	6.2 and 6.3	Rewording of objective 4 Editorial checks Clarification of the stratifications performed Clarification
4	30th October 2020	7.0	Editorial checks
5	30th October 2020	7.2.2	Removal of ≥ 18 criteria, pediatric patients allowed Comment from reviewer
6	30th October 2020	7.2.2	Change of 365 to 120 days prior exposure to corticosteroids for determining naïve and prevalent users and also removed from hospital cohort in figure 1 hospitalization cohorts
7	30th October 2020	7.2.3	Follow up period has been changed from 180 days to 90 Error corrected

8	30th October 2020	7.3.1	Update of alternative COVID-19 definitions using CDC and WHO guidelines	In line with the amended objective 4 and alternative methodology
9	30th October 2020	7.7.5	Further information of use of propensity score adjustment strategy.	Further details requested
10	30th October 2020	7.7.6	A new method is proposed to assess the performance of various COVID-19 definitions probabilistic diagnostic predictive model	Comment from the reviewer
11	30th October 2020	7.7.7	New section on Meta-analysis added	Comment from the reviewer
12	16 th November 2020	7.2.2	Hospitalization 30 days after diagnosis allowed	Comment from the reviewer
13	16 th November 2020	7.1	Figure 1 updated with the new inclusion criteria	Comment from the reviewer
14	16 th November 2020	7.2.4	Starting dose of steroids was added as a subgroup	Comment from the reviewer
15	16 th November 2020	7.3.2	Define the low and high dose categories	Comment from the reviewer
16	16 th November 2020	7.7.8	A sensitivity analysis to exclude short term use corticosteroid users was added	Comment from the reviewer
17	16 th November 2020	7.9.1	Some limitations were added	
18	4 th December 2020		Abstract amended to align with the protocol Misspellings and editorial checks across the entire protocol	

Section 4.0 Milestones

Milestone	Planned date
Milestone	Planned date
Study protocol submitted	20 th September 2020
Approval Study Protocol by EMA	23 th November 2020
Registration in the EU PAS register	October 2020
Start of data collection	NA. Data extraction start date is 1st January 2020
End of data collection	NA. Data extraction last end date will be the latest available date in each database up to maximum 1st January 2021
Final study report provided to EMA	April 2021

Section 5.0 Rationale and Background

Coronavirus disease 2019 (COVID-19) caused by Severe Acute Respiratory Syndrome Corona virus 2 (SARS-CoV-2) originated in China in December 2019 and was accepted as a global pandemic March 2020. (1) The majority of COVID-19 infections are either asymptomatic or have mild symptoms, however, progression to pneumonia and acute respiratory distress syndrome (ARDS) is reported in 10-20% cases, especially in those of older age or with co-morbidities who are subsequently more likely to be hospitalized and require ventilatory support. (2,3) The overall case fatality rate is hard to estimate in view of rapidly changing data and serious underestimation of cases, however, it is considered to be around 3%. (4) Amongst COVID-19 patients admitted to UK hospitals, the case fatality rate is over 26% overall, and over 37% in patients requiring invasive mechanical ventilation. (5)

According to the current literature, older age and co-morbidities are associated with higher risk of immunologic complications such as macrophage activation syndrome (MAS) and cytokine storm syndrome secondary to, and disproportionate to the severity of Covid-19 infection. (6) Accordingly, there are recommendations that anti-viral treatment should be combined with appropriate immunosuppressive and immunomodulatory drugs since it is hypothesized that early recognition and appropriate treatment of immunologic complications will decrease the morbidity and mortality in COVID-19 patients. (7)

With regards to treatment options, there are many immunosuppressive and immunomodulatory drugs which may be repurposed. Initially antimalarial drugs (chloroquine and hydroxychloroquine) were reported to have immunomodulatory effects and antiviral activity and beneficial effects among patients with COVID-19 (8), however, serious concerns have been raised about the results of clinical trials on these products.(9) Other classes of drugs that show potential include interleukin (IL)-6R antagonists, IL-1 antagonists, TNF-alpha inhibitors, and Janus kinase inhibitors. (10,11) Systemic glucocorticoid use in ARDS is controversial, however, some positive results have been reported for dexamethasone. (12–14). Until March 2020 systemic glucocorticoid use was not recommended for routine use by the WHO except in patients with lethal complications, because of a lack of positive evidence from randomized controlled trial (RCTs). (15) More recently, the RECOVERY RCT has shown a significant reduction of death in COVID-19 patients treated with dexamethasone by 35% in ventilated patients and by 20% amongst patients on supplemental oxygen therapy, however no benefit was observed in mild cases.(13,16)

Several literature reviews have attempted to summarize existing evidence. Lu et al. performed a review addressing use of steroids in critically ill COVID-19 patients to explore whether these drugs may reduce mortality, however for patients with severe COVID-19 without ARDS the evidence remains inconsistent. (17) Another systematic review (11) found 5 studies on the role of steroids for COVID-19 reporting inconsistent outcomes. Of the 5 studies (4 retrospective studies and 1 quasi-prospective study) conducted for evaluating the role of glucocorticoids, 3 studies have shown benefit, while 2 studies showed no benefit and there was a suggestion of significant harm in critical cases in one sub-study.

A lot of questions remain unanswered, especially which patients might benefit from glucocorticoids use, what is the best substance and dose (7) and timing of administration. (18) Some US and UK guidelines now recommend to low-dose glucocorticoid therapy (“shock-reversal”), over no glucocorticoid therapy and only in severe patients, however the evidence is considered weak. (19)

The current study aims to partially answer some of the remaining questions as detailed in the following sections.

Section 6.0 Research Questions and Objectives

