6.2 Primary Objective

To describe utilization of systemic glucocorticoids (e.g., dexamethasone, prednisolone, methylprednisolone or hydrocortisone) for treatment of COVID-19 in two settings: hospitalized (in hospital care) and ambulatory (any care received outside of hospital) within 90 days following COVID-19 diagnosis. The following variables will be described:

- Prevalent use or naïve (incident) use of systemic glucocorticoid at date of diagnosis of COVID-19
- Concomitant use of other medications (number and type) and invasive/non-invasive respiratory support during follow up
- Type of systemic glucocorticoid received
- Time to systemic glucocorticoid initiation from COVID-19 diagnosis
- Route of administration
- Systemic glucocorticoid daily dose at initiation (treatment index date), cumulative duration, distribution of duration of use and cumulative dose of systemic glucocorticoid received
- For prevalent users: proximity of previous glucocorticoid use to COVID-19 diagnosis (current use (concomitant on date of COVID-19 diagnosis, recent use (between 15-30 days before date of COVID-19 diagnosis) or remote use (use ended more than 30 days before date of COVID-19 diagnosis))

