7.3.2.1 Glucocorticoids

Glucocorticoids used in COVID-19 indication

The primary treatment group of interest is based on exposure to systemic glucocorticoids. The following drugs will be considered as being used for COVID-19 diagnosis:

- Dexamethasone (H02AB02)
- Prednisone (H02AB07)
- Prednisolone (H02AB06)
- Methylprednisolone (H02AB04)
- Hydrocortisone (H02AB09)

Only glucocorticoids which were investigated in clinical trials (13,21) or are recommended by clinical guidelines are included (22–24) to avoid misclassification of steroids used for other conditions. As indication is not captured in the available databases, a glucocorticoid treatment will be considered to have been initiated for COVID-19 treatment if:

For incident users

- The glucocorticoid treatment was initiated between 2 before and 30 days after COVID-19 diagnosis date (21)
- It is one of the five glucocorticoids recommended for COVID-19 as above

For prevalent users

- The glucocorticoid treatment was initiated between 2 before and 30 days after COVID-19 diagnosis date
- It is one of the five glucocorticoids recommended for COVID-19 as above
- The glucocorticoid started after COVID-19 diagnosis differs from the chronically used glucocorticoids OR there is a change in dose or schedule of administration compared to the prevalent use, occurred after COVID-19 diagnosis.

Glucocorticoids for pre-existing conditions

For the prevalent users, any steroid in the ATC class H02 glucocorticoids for systemic use will be considered. A patient is defined as a systemic glucocorticoids prevalent user if it has at least one prior exposure to systemic² glucocorticoids in the 120 days prior to diagnosis index date.

For the description of prevalent users of glucocorticoids, categories of use will be created based on proportion of days covered (PDC) during the lookback period. PDC is calculated as the number of days in period covered by prescriptions divided by number of days in the period.

- PDC > 85% as heavy user
- PDC 50-85% as moderate user
- less than 50% PDC as light user

Another categorization of prevalent glucocorticoids user will be based on how recently in the past the last prescription was observed:

- current use (concomitant on date of COVID-19 diagnosis)
- recent use (between 15-30 days before date of COVID-19 diagnosis)
- remote use (use ended more than 30 days before date of COVID-19 diagnosis)

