Steroids often have adjusted dose regimens such that drug may be slowly increased or decreased over time and short acute treatment episodes are also possible. Such changes in dose over time will not be examined, however total cumulative dose will be examined in relation to outcomes of interest (see below).

Cumulative dose

For glucocorticoids used in COVID-19 indication, orally administered, if quantity is available, the formula to calculate the cumulative exposure in mg is described below:

$$Cumulative\ dose_{solid}[mg] = \sum_{all\ exposures} quantity \times amount_value [mg]$$

If the **quantity is missing**, the number of units per day for solid formulations are extracted. The cumulative exposure in mg can then be calculated using the following formula:

$$Cumulative\ dose_{solid}[mg] = \sum_{exposures} units\ per\ day \times amount_value [mg] \times duration$$

For intravenous administration (bolus administration), the dose administered each time will be counted.

$$Cumulative\ dose\ intravenous [mg] = \sum_{all\ exposures} amount_value [mg]$$

Exposure groups for incidence calculation (secondary objective 2 and 3)

For the incidence rates calculation, an on-treatment exposure will be considered with mutually exclusive groups to allow calculation of incidence rates.

Each person will be classified as belonging to one of the following mutually exclusive exposure groups at treatment index date following COVID-19 diagnosis:

- Use of systemic glucocorticoids without other treatments for COVID-19 (drug and respiratory support)
- Use of systemic glucocorticoids plus other treatments for COVID-19 (drug and respiratory support)
- Only other treatments and respiratory support with no systemic glucocorticoids

- No specific treatments for COVID-19 infection (other concomitant treatments for indications other than for COVID-19 are allowed)

A single prescription would be enough to consider the patient as exposed. See section 7.3.2.1 for description of 'other treatment for COVID-19' that are included.

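### A patient newly started on a systemic glucocorticoid outside the five-drug list has no stated place in the four exposure groups, and by the rules falls into group 3 (labelled as without systemic glucocorticoids) or unseen into group 4

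*Protocol*

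**What the plan says.** The primary objective (Section 6.2) is "To describe utilization of systemic glucocorticoids (e.g., dexamethasone, prednisolone, methylprednisolone or hydrocortisone) for treatment of COVID-19 in two settings"; the drug names there are examples. One of the items to be described is the type of systemic glucocorticoid received.

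The abstract (Section 2.0, Variables) gives the exposure as a closed list: "Glucocorticoids used in COVID-19 indication glucocorticoid (dexamethasone, prednisolone, prednisone, methylprednisolone or hydrocortisone". The operative rule is in Section 7.3.2.1. It introduces five substances with "The following drugs will be considered as being used for COVID-19 diagnosis" and makes membership of that list a required condition for incident and prevalent users alike: "It is one of the five glucocorticoids recommended for COVID-19 as above". The start must also fall between 2 days before and 30 days after diagnosis. Prevalent users must in addition show a change of substance, dose or schedule. The section gives its reason: only drugs studied in trials or recommended by guidelines "are included (22–24) to avoid misclassification of steroids used for other conditions". Its premise is "As indication is not captured in the available databases".

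For use before diagnosis the same section is wider: "any steroid in the ATC class H02 glucocorticoids for systemic use will be considered".

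Section 7.3.2.3 requires each person to be placed in one of four mutually exclusive groups. Group 3 is "Only other treatments and respiratory support with no systemic glucocorticoids". Section 7.7.4 also labels it as having no steroids. Group 4 is defined by the absence of specific treatment for COVID-19, with drugs for other indications allowed.

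**The concern.** The list answers one question: may this steroid be credited to COVID-19? The exposure groups ask another: is this person on a systemic glucocorticoid? The protocol uses the first answer for the second question. A person who starts an off-list systemic glucocorticoid after diagnosis is not counted as a glucocorticoid user in any group.

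This matters because the adverse events in Section 7.3.3 include recognised steroid effects such as hyperglycaemia, infection, gastrointestinal bleeding, psychosis and myopathy, and rates are reported separately for each group. Section 7.7.8 speaks of a reference group for incidence rates, so readers are likely to take groups 3 and 4 as background. Events that occur on an off-list steroid would then be part of that background. The limitations in Section 7.9 do not mention this.

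**Working it through.** The protocol states no figure for this point, so the check is a trace of the rules, followed by an illustration of size.

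**Trace for a patient who starts an H02 glucocorticoid that is not one of the five**

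1. Day of start. A start on day -2 or day -1 is H02 exposure before diagnosis and makes the patient a prevalent user. The naive case therefore runs from day 0 to day +30.
2. COVID-19 glucocorticoid? No. The five-drug condition in Section 7.3.2.1 fails, so groups 1 and 2 are closed to this patient.
3. Other COVID-19 treatment? Not through the steroid. Appendix 3 contains no H02 drug.
4. With an Appendix 3 drug or respiratory support, the patient goes to group 3. The label says no systemic glucocorticoids, which is untrue of this patient. If the label is applied literally instead, the patient fits none of the four groups, although each person must have one.
5. With neither, the patient goes to group 4. That label does not claim freedom from steroids, so it is not false, but the steroid cannot be seen.
6. Boundary. An off-list drug taken the day before diagnosis makes the patient a glucocorticoid user. The same drug started the day after counts as none.
7. Censoring. Sections 7.3.2.3 and 7.7.4 censor at a switch to another treatment, including another glucocorticoid. They do not say whether that means the five drugs or all of H02.
8. Prevalent users who continue a steroid unchanged also fail the Section 7.3.2.1 conditions. They reach groups 3 and 4 in the same way and raise the same label problem.

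**Illustration of size**

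Inputs, both assumed because the documents give neither: p, the share of naive patients who start any H02 drug; s, the share of those starts that are off-list. Off-list starters are taken not to start a listed drug as well.

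- Counted as on a COVID-19 glucocorticoid: p(1 - s).
- Share of groups 3 and 4 combined who are on an off-list steroid: c = p·s / [1 - p(1 - s)].

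| p | s | p·s | 1 - p(1 - s) | c |
|---|---|---|---|---|
| 0.10 | 0.05 | 0.005 | 0.905 | 0.55% |
| 0.10 | 0.15 | 0.015 | 0.915 | 1.64% |
| 0.10 | 0.30 | 0.030 | 0.930 | 3.23% |
| 0.20 | 0.30 | 0.060 | 0.860 | 6.98% |

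If the off-list steroid multiplies an event rate by RR, the rate in the combined groups is multiplied by 1 + c(RR - 1). With an assumed RR of 2, c = 0.55% gives 1.0055 and c = 3.23% gives 1.032. The split between groups 3 and 4 is unknown, so the share in group 3 alone may be higher or lower than c.

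**The case against.** The strongest reply is that the list is deliberate. The objective is limited to use for treatment of COVID-19, and where indication is treated as unavailable, a closed list buys specificity. Using all of H02 for prior use serves another purpose, namely deciding who is naive, so the difference in breadth is not in itself a contradiction. This stands, and the list should stay for attribution. It does not extend to counting a newly started systemic glucocorticoid as none.

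A second reply is that group 4 openly allows drugs for other indications. That stands as far as the label goes. On the protocol's own premise, though, nobody can know that an off-list steroid started after diagnosis was for something else. The premise is also not uniform: Section 7.4 lists indication among the recorded items for LPD Italy and IPCI.

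A third reply is low impact. Comparison between treated and untreated patients is out of scope (Section 6.3), the Cox models are run within groups, and the table above implies changes of a few per cent at most for p = 10%. This limits the consequence to labels and descriptive rates. Those rates are nevertheless the product of objectives 2 and 3.

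A fourth reply is that the primary objective also describes concomitant medication, where off-list use might appear. It might, but nothing requires it to be shown there or linked to the exposure groups.

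A reader might infer more than the documents support:

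- That such a patient is both reported as untreated and placed in the group labelled glucocorticoid-free. These are groups 4 and 3, and one patient cannot be in both.
- That COVID-19 glucocorticoid use is understated by the fraction s. That holds only for starts of any H02 drug. For use against COVID-19 it is an upper bound.
- That differences between countries are artefacts of the list. Off-list prescribing that differs by country could contribute, but the documents give no figure.
- That the list deprives these patients of a treatment index date. Section 7.2.3 defines that date only by a COVID-19 glucocorticoid start, so all of groups 3 and 4 lack one.

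**Conclusion.** The concern holds for classification and labelling, not for the choice of list. The placement of new off-list H02 starters is left unstated. The rules put them in group 3 under a label that is then wrong, or in group 4 where they cannot be identified. Adverse events on those drugs enter the rates of both groups, and the type description is confined to five substances despite the open wording of the objective.

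The size is unknown. Under the assumptions p = 10% and s from 5% to 30%, it is about 0.55% to 3.2% of groups 3 and 4 combined, and about 7.0% with p = 20% and s = 30%. The effect on rates is probably modest. The change is still worth making because it is cheap and the present labels cannot be taken at face value.

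**What to change.** 1. Section 7.3.2.1: keep the five-drug list for attribution to COVID-19. Add to objective 1 a report of new off-list H02 starts in the attribution window, by substance and database, shown separately from COVID-19 glucocorticoid use.
2. Section 7.3.2.3: define group 3, and any steroid-free reading of group 4, by absence of a newly started H02 drug at the group's index date. Put off-list starters in a row of their own.
3. Sections 7.3.2.3 and 7.7.4: censor groups 3 and 4 when an H02 substance is newly started during follow-up. Do not censor at refills of unchanged prevalent use, since a rule based on any H02 record would remove prevalent users at their next routine prescription.
4. Label or report separately the prevalent users in groups 3 and 4 who continue a steroid unchanged, and use the same group 3 label in every section.

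Cost: a few sentences, two or three table rows, and slightly fewer patients and less person-time in groups 3 and 4. The H02 concept set is already needed for the prevalent-user definition.
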